5.2.2.1.2 Time to death over 52 weeks

Date of death for an individual patient will be obtained from either the AE reporting page for patients with AEs leading to death or from the vital status assessment eCRF page.

For patients with known date of death (regardless of the cause of death) within the first 52 weeks the derivation will be as follows:

- Time to death [days] = Date of death – date of first drug intake + 1

Patients who did not experience any event within the first 52 weeks will be censored according to the mechanism for censoring as described in Table 5.2.2.1.2: 1 below.

Table 5.2.2.1.2: 1 Censoring Rules for Time to death over 52 weeks

Rule #	Situation	Outcome (event or censored)	Date of event or censoring
1	Patient died within the first 52 weeks and date of Death is known	Event	Date of event
2	Patient died within the first 52 weeks and date of Death is unknown	Event	Imputed date of event
3	Patient is alive after 52 weeks	Censored	Day 373 (372 days after first drug intake)
4	Patient status is unknown	Censored	Date of last contact when the patient was known to be alive

5.2.2.1.3 Time to first acute ILD exacerbation or death over 52 weeks

Acute ILD exacerbation is defined in the CTP as an acute, clinically significant, respiratory deterioration characterized by evidence of new widespread alveolar abnormality with all of the following:

- Previous or concurrent diagnosis of ILD
- Acute worsening or development of dyspnoea typically less than one month duration
- Computed tomography with new bilateral ground-glass opacity and/or consolidation superimposed on a background pattern consistent with fibrosing ILD
- Deterioration not fully explained by cardiac failure or fluid overload

Events that are clinically considered to meet the definition of acute exacerbation but fail to meet all four diagnostic criteria due to missing CT data should be termed “suspected acute exacerbations”. Please note that only acute ILD exacerbations that fulfil all the criteria depicted above will be taken into account and contribute to the endpoint. Information on acute ILD exacerbations will be obtained from the Adverse Events page.

For those patients who either experience acute ILD exacerbations or who die due to any cause within the first 52 weeks, time to first acute ILD exacerbation or death [days] will be computed as:

- Earliest of date of first documented acute ILD exacerbation or death – date of first drug intake + 1

Patients who did not experience any ILD exacerbation event within the first 52 weeks will be censored according to the mechanism for censoring as described in [Table 5.2.2.1.3: 1](#).

Table 5.2.2.1.3: 1 Censoring Rules for Time to first acute ILD exacerbation or death over 52 weeks

Rule #	Situation	Outcome (event or censored)	Date of event or censoring
1	Patient had a documented acute ILD exacerbation or died within the first 52 weeks and the date of the event is known	Event	Earliest Date of event
2	Patient had a documented acute ILD exacerbation or died within the first 52 weeks and the date of the event is unknown	Event	Imputed date of event
3	Patient did not have a documented acute ILD exacerbation and is alive after 52 weeks	Censored	Day 373 (372 days after first drug intake)
4	Patient status is unknown	Censored	Date of last contact when the patient was known to be alive and event free

5.2.2.2 Other secondary efficacy endpoints

5.2.2.2.1 Time to death due to respiratory cause over 52 weeks

Analysis of time to death due to respiratory cause will be based on the adjudicated cause of death as determined by an independent Adjudication Committee (AC). The AC will review all fatal cases and adjudicate all deaths to either cardiovascular, respiratory or other causes.

For those patients who died, and whose death is attributed to respiratory causes within the first 52 weeks by the AC, time to death due to respiratory cause [days] will be computed as:

- Date of death – date of first drug intake + 1

Patients who did not experience any event within the first 52 weeks will be censored according to the mechanism for censoring as described in [Table 5.2.2.2.1: 1](#).

Table 5.2.2.2.1: 1 Censoring Rules for Time to death due to respiratory cause over 52 weeks

Rule #	Situation	Outcome (event or censored)	Date of event or censoring
1	Patient died within the first 52 weeks due to respiratory cause and the date of the event is known	Event	Date of event
2	Patient died within the first 52 weeks due to respiratory cause and the date of the event is unknown	Event	Imputed date of event
3	Patient is alive after 52 weeks	Censored	Day 373 (372 days after first drug intake)
4	Patient status is unknown	Censored	Date of last contact when the patient was known to be alive

5.2.2.2.2 Time to progression or death over 52 weeks

Progression is defined as the date when $\geq 10\%$ of absolute decline in FVC % pred compared to baseline occurs for the first time.

For those patients who fulfil the criteria for progression or death due to any cause within the first 52 weeks, time to progression or death due to any cause [days] will be computed as:

- Earliest of date of documented progression event or death – date of first drug intake + 1

Patients who did not experience any event within the first 52 weeks will be censored according to the mechanism for censoring as described in [Table 5.2.2.2.2: 1](#).

Table 5.2.2.2.2: 1 Censoring Rules for Time to progression or death over 52 weeks

Rule #	Situation	Outcome (event or censored)	Date of event or censoring
1	Patient had a documented progression or died within the first 52 weeks and the date of the event is known	Event	Earliest Date of event
2	Patient had a documented progression or died within the first 52 weeks and the date of the event is unknown	Event	Imputed date of event
3	Patient did not have a documented progression and is alive after 52 weeks	Censored	Day 373 (372 days after first drug intake)
4	Patient status is unknown	Censored	Date of last contact when the patient was known to be alive and event free

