- The next visit will be scheduled and prepared.

Visit 7, Visit 9 and EOT_A ('big visits') procedures

At Visit 7, Visit 9 and EOT_A (primary endpoint visit), the same procedures will be performed as done at baseline Visit 2. Exceptions are the typical randomization measures, e.g. eligibility review, medical history assessment and randomization as well as DNA banking sample which is only taken once. In addition, if EOT takes place before Visit 7, HRCT should not be repeated. For Visit 7, Visit 9 and EOT_A always refer to the [Flowchart Part A](#).

General rules

- Treatment compliance will be reviewed by site personal.
- Trial medication will be collected and/or dispensed according to Flowcharts Part A.
- Visit 9 and end of treatment visit (EOT_A) are identical visits. EOT_A is to be used in eCRF at any time a patient ends trial medication (scheduled or prematurely).
- Patient who prematurely discontinued trial medication will attend all originally planned visits until the end of the trial (except for the laboratory visits 6a, 7a and 8a).
- IRT should always be notified on end of treatment (EOT).
- Vital status will be collected for patients who prematurely discontinued trial medication and failed to attend future visits as planned, as well as for those who did not attend scheduled visits as planned at week 52 (scheduled Visit 9/EOT_A).
- PROs will always be scheduled prior to any other procedure and in the above described order and will be reviewed for completeness by site personal.
- Drug intake at visit days should always be performed at site and after blood and urine sample collection and pregnancy test.
- FlowScreen® spirometry (FVC) and DLCO measurements will always be in the allowed time window and the described order (reference visit = Visit 2).
- Non-elective hospitalization will be recorded.
- Acute ILD exacerbations will be recorded.
- Resting 12-lead electrocardiogram using site's own equipment will be performed and evaluated (if possible prior to blood draw).
- At Visit 7, a PK sample will be collected. The patient needs to record exact date and clock time of medication intake the preceding three days on a PK-card provided at

Visit 6. The date and time of blood collection for PK and drug administration at the site will be recorded.

- Biomarker blood sampling will be done. The date and time of blood collection for biomarker samples will be recorded in the eCRF.

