7.5 HANDLING OF MISSING DATA

7.5.1 Efficacy Endpoints

The effect of missing data on the primary endpoint will be investigated using multiple imputation techniques.

For the primary endpoint, for each co-primary analysis population, the following subsets of patients will be defined:

1. Patients with an FVC result at week 52 who received trial medication until week 52.
2. Patients with an FVC result at week 52 who prematurely discontinued trial medication prior to week 52.
3. Patients without an FVC result at week 52 who were alive at week 52.
4. Patients without an FVC result at week 52 who died prior to week 52.

These four subsets of patients will be used in sensitivity analyses to estimate the treatment effect under differing assumptions around the persistence of efficacy after withdrawal of trial medication. [Table 7.5.1: 1](#) describes the planned sensitivity analyses for handling missing primary endpoint data. Sensitivity analyses 1 and 2 will only be performed if there are at least 10 patients included in patient subset 2 in each treatment group.

Table 7.5.1: 1

Sensitivity analyses for handling missing primary endpoint data

Analysis	Patient subset 3: No FVC result but alive at Week 52		Patient subset 4: No FVC result and died prior to Week 52	
	Handling of missing FVC result	Underlying assumption	Handling of missing FVC result	Underlying assumption
Primary analysis	Missing data handled by model.	Assumes missing at random. Discontinued patients would have behaved similarly to patients who did not discontinue.	Missing data handled by model.	Assumes missing at random. Discontinued patients would have behaved similarly to patients who did not discontinue.
Sensitivity analysis 1	Based on the slope estimates for drug and placebo in patient subset 2.	Patients without a result would have behaved similarly to discontinued patients with a result who are in the same treatment group.	Based on the slope estimates for placebo patients in patient subset 2, but truncated so that those who died are more severe.	Patients who died before week 52 would have behaved in a similar or worse way to a placebo patient who prematurely discontinued.
Sensitivity analysis 2	Based on the slope estimates for placebo in patient subset 2.	Patients without a result would have behaved similarly to discontinued placebo patients with a result.		

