5. ENDPOINTS

In this section, more details are given regarding endpoints. Note that for all endpoints and analyses, [Section 6.7](#) should be consulted for baseline value definition. For analyses that are specified over 52 weeks (Part A), unless otherwise specified, all data (including baseline) up to week 52 (inclusive – as defined in [Section 6.1](#)) will be taken into account, including follow-up visits before week 52 for patients who discontinue the trial medication prematurely. Analyses over the whole trial (Part A and Part B) reported at the time of the benefit-risk analysis will be based on all data collected until the data cut-off for DBL1. Analyses over the whole trial (Part A and Part B) reported after the final database lock (DBL2) will be based on all data collected within the trial.

Handling of missing data points is described in [Section 6.6](#).

For endpoints where the “date of last contact” is utilised, the following will apply:

- The last contact date when the patient was known to be alive is defined as the latest date recorded in the electronic Case Report Form (eCRF) from the dates listed below (in case a date is planned to be imputed for the analysis, the imputed date will also be used for the definition of “date of last contact”):
 - Date of last visit (e.g. for spirometry), data of last reported Adverse Event (AE) (excluding censored dates), date of last reported concomitant treatment, date of last laboratory sample, date of last drug intake, date of last reported dose change / interruption, last contact date (as documented on the termination of trial eCRF page if the reason for not completing the planned observation period is NOT “Death”), vital status date (from the vital status eCRF page if the patient is known to be alive) and the latest of vital status date / last successful contact date (from the vital status eCRF page if the patient was lost to follow-up).

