5.3.2.5 Time to progression or death over the whole trial

Progression is defined as the date when $\geq 10\%$ of absolute decline in FVC % pred occurs for the first time. For those patients who progressed or died due to any causes within the trial, time to progression or death due to any cause [days] will be computed as:

- Earliest of date of documented progression event or death – date of first drug intake + 1

Patients who did not experience any event will be censored at the date of last contact when the patient was known to be alive and was known not to have progressed.

Patients who did not experience any event during their trial participation will be censored according to the mechanism for censoring as described in Table 5.3.2.5: 1.

Table 5.3.2.5: 1 Censoring Rules for Time to progression or death over the whole trial

Rule #	Situation	Outcome (event or censored)	Date of event or censoring
1	Patient had a documented progression or died and the date of the event is known	Event	Earliest Date of event
2	Patient had a documented progression or died and the date of the event is unknown	Event	Imputed date of event
3	Patient did not have a documented progression and is alive	Censored	Date of last contact when the patient was known to be alive and event free
4	Patient status is unknown	Censored	Date of last contact when the patient was known to be alive and event free

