6.6.2.2 Time-to-event endpoints

In the analyses of the time-to-event endpoints, missing or incomplete data will be managed by standard survival analysis techniques (i.e. censoring).

For the time to first acute ILD exacerbation, or first non-elective hospitalization in case of partially missing dates, the following imputation will be done:

- If day is missing, then imputed day will be the 15th of the month
- If day and month are missing, then imputed date will be the 1st of July of the (non-missing) year
- If year is missing, date will not be imputed

A missing or incomplete date of death will be imputed/completed so that the derived date is the earliest possible date which is on or after date of onset of the fatal AE, and on or after treatment start (in case this AE is treatment emergent), and on or after date of last contact.

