7.4.2.1.2 Sensitivity to missing data handling

To investigate the potential impact of missing data on the treatment effect, patients will be classified into different patterns depending on the availability of data:

- Patients with a 52 week FVC value (see [Table 6.1.1: 1](#) for further information regarding the analysis period):
 1. Those who received trial drug until 52 weeks (defined as patients who did not prematurely discontinue the trial medication before 52 weeks according to the “end of trial medication” page of the eCRF) (pattern 1)
 2. Those who prematurely discontinued trial drug before 52 weeks (as per information given on the “end of trial medication” page of the eCRF) but who were followed up until week 52 (pattern 2)
- Patients without a 52 week FVC value:
 3. those who were alive at 52 weeks (based on “vital status” page of the eCRF, and no fatal AE recorded on the “adverse event” page of the eCRF) (pattern 3)
 4. those who died before 52 weeks (based on “vital status” page of the eCRF, or fatal AEs recorded on the “adverse event” page of the eCRF) (pattern 4)

These four patterns will be used in sensitivity analyses to estimate the treatment effect under differing assumptions regarding the persistence of efficacy post withdrawal of randomised

treatment. As described hereafter, three resulting alternative analyses will be defined. See an overview in [Table 7.4.2.1.2: 1](#).

Multiple imputation will be used to handle missing data at week 52. Non-monotone missing data and/or missing data at visits before week 52 will not be imputed. The imputation model will be similar to the statistical model of the primary analysis (see [Section 7.4.1](#)).

The number of imputations will be set to 1000 in order to ensure adequate efficiency for the estimation of missing data. For each imputed dataset, the same statistical model as defined for the primary analysis will be used for the analysis as depicted in [Section 7.4.1](#). The results will be pooled following the standard multiple imputation procedure (16). See also [Section 9.5.3](#) for further technical information on the implementation of the multiple imputation approach.

Table 7.4.2.1.2: 1 Primary and sensitivity analyses for handling of missing data

Analysis	Pattern 3: Missing week 52 data in patients still alive at 52 weeks		Pattern 4: Missing week 52 data in patients who died before 52 weeks	

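### Time to progression or death over 52 weeks: survivors whose spirometry stopped early are censored as progression-free at Day 373, and Rules 3 and 4 can overlap

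*SAP*

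**What the plan says.** SAP 5.2.2.2.2 defines progression as the first absolute fall of at least 10% in FVC % predicted from baseline, and combines it with death from any cause. In Table 5.2.2.2.2: 1:

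- Rule 3 applies when "Patient did not have a documented progression and is alive after 52 weeks" and censors at Day 373.
- Rule 4 applies when the patient's status is unknown and censors at "Date of last contact when the patient was known to be alive and event free". The SAP does not define status.

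Other parts of the plan bear on this:

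- Protocol 6.2.2: "Vital status will be collected for patients who prematurely discontinued trial medication and failed to attend future visits as planned". Footnote 15 of the Part A flow chart seeks week-52 vital status for every randomized patient.
- Protocol 7.5.1, subset 3: "Patients without an FVC result at week 52 who were alive at week 52". SAP 7.4.2.1.2 has the same group as pattern 3, under "Patients without a 52 week FVC value", with survival taken from the vital-status page.
- SAP 5 lists the vital-status date among the dates that count as last contact.
- SAP 6.6.2.2 handles missing time-to-event data by censoring, without naming a date.
- SAP 5.3.2.5, the whole-trial version of this endpoint: a patient without an event "will be censored at the date of last contact when the patient was known to be alive and was known not to have progressed".

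Rule 3 has the same form in the tables for exacerbation or death (5.2.2.1.3: 1) and hospitalisation or death (5.3.1.1: 1).

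**The concern.** Rule 3 treats the absence of a documented progression as the absence of progression. That is sound for a patient with spirometry up to week 52, and Day 373 is then a proper end date. It is not sound for a patient who stopped attending and is known only to be alive, and the plan expects such patients.

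If status in Rule 4 means vital status, Rules 3 and 4 are exclusive and Rule 3 sends every unassessed survivor to Day 373. If it means event status, as the date cell of Rule 4 suggests, the same patient meets both rules and has two censoring dates. Either way, unobserved time can be counted as progression-free, and two programmers could derive different data sets.

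This endpoint carries no p-value (SAP 4.3), so the hazard ratio, its confidence interval and the Kaplan-Meier curves are the whole reported result.

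**Working it through.** **The plan's own figure.** Under the SAP formula (date minus date of first intake, plus 1), 372 days after first intake is day 372 + 1 = 373. This is also the last day of the week-52 FVC window, days 310 to 373 (Table 6.7: 1).

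**One patient.** Last FVC at week 12 (day 85), no progression, alive by telephone at week 52. Rule 3 credits 373 days. Censoring at the last FVC credits 85. The difference is 373 − 85 = 288 days, or 288/373 = 77% of the credited time.

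**Do other passages settle it?** In the time-to-death table (5.2.2.1.2: 1) Rule 4 asks only that the patient be known alive. There vital status is event status, so the template works. The composite tables add event-free to the Rule 4 date but leave the situation cell unchanged. Table 6.1.1: 1 ends the 52-week efficacy period at the last measurement, but does not override an explicit Day 373 cell. Date of last contact does not help, because an adverse-event, medication or vital-status entry extends it without an FVC.

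**Size, by simulation.** The documents give neither the loss of spirometry nor the progression risk for this trial, so these are assumptions: one-year progression risk 20% to 40%; placebo deaths 7.8% (pooled IPF trials, Protocol 1.2); either no effect, or hazard ratios of 0.6 for progression and 0.7 for death. Progression is seen only at attended visits (days 15, 29, 43, 85, 169, 253, 365), all deaths to day 373 are known, and spirometry stops at a uniform time over the year, unrelated to prognosis. There are 3 million patients per arm, with Cox regression using Breslow ties. The entries are the percentage shift of the hazard ratio from complete follow-up.

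| Loss, nintedanib/placebo (%) | Rule 3 | Censor at last FVC, deaths kept |
|---|---|---|
| 6/4 | −0.7 to −1.0 | +0.2 to +0.5 |
| 10/5 | −2.0 to −2.7 | +0.4 to +1.1 |
| 19/13 | −2.3 to −3.2 | +0.6 to +1.5 |
| 10/10 | 0.0 to +0.3 | 0.0 to +0.2 |

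For Rule 3 the shift is −3.1% to −4.5% at 10/5 if all loss falls in the first 90 days, and −6.2% to −7.9% at 20/5. At 20/5 with 30% progression risk and no effect, Rule 3 gives −7.3% and the fix +2.0%.

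**Displayed risk.** True value 35.0% in both arms:

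| Loss (%) | Rule 3 | Fix |
|---|---|---|
| 6/4 | 34.1/34.4 | 35.2/35.1 |
| 10/10 | 33.4/33.4 | 35.3/35.3 |
| 19/13 | 32.0/32.9 | 35.6/35.3 |

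A hand check agrees. With uniform loss of a fraction L, about L/2 of the progressions go unseen. At 30% progression risk and L = 10%, that is 30% × 0.05 = 1.5 points, and 35.0 − 1.5 = 33.5%. For the hazard ratio at 6/4, ln(1 − 0.341)/ln(1 − 0.344) = 0.4170/0.4216 = 0.989, against a simulated shift of −1.0%.

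**Loss related to prognosis.** With a shared gamma frailty (variance 1), 30% progression risk and hazard ratios 0.6 and 0.7, the complete-follow-up hazard ratio is 0.668. The shifts at 6/4, 10/5 and 19/13 are:

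- Rule 3: −1.7%, −4.1%, −5.7%
- Last FVC, deaths kept as events: −0.6%, −1.4%, −2.0%
- Last FVC, late deaths also censored: −1.0%, −2.3%, −3.4%

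**A second, smaller simulation** (30,000 per arm, 7% placebo deaths, 30% to 45% event risk) points the same way. With 20% loss on nintedanib, 10% on placebo and no true effect, the hazard ratio was 0.936 to 0.948 under Rule 3, 0.999 to 1.012 with last-FVC censoring and 0.996 to 1.009 with complete follow-up.

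**Against sampling error.** SE of log HR ≈ 2/√events: 0.163, 0.138 and 0.122 at 150, 210 and 270 events. A 3% shift is |ln 0.97| = 0.030, and 0.030/0.138 ≈ 0.2 SE.

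**The case against.** The strongest case is that this is a small ambiguity. Patients who stop drug are asked to attend all visits, including spirometry, so few survivors may lack a late FVC. No loss rate is documented. The 19/13 pattern borrows the IPF figure for adverse events leading to treatment discontinuation (Protocol 1.2), which is not loss of spirometry, and the direction of the imbalance is assumed too. At 6/4 the shift is below 0.1 SE. The closely related binary endpoint (absolute decline above 10% at week 52) already counts missing patients as worst case, so readers see an opposite assumption. The whole-trial comparison is imperfect, because its last-contact date is not clearly tied to FVC either.

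The remedy also has limits. A patient with an FVC on day 310 would still be credited with 373 − 310 = 63 unobserved days. Keeping deaths as events while censoring survivors at the last FVC makes censoring depend on outcome and slightly overstates risk (35.6% against 35.0% at 19% loss). Under loss unrelated to prognosis, censoring late deaths as well comes closer (+0.1%, +0.3% and +0.4% against +0.2%, +0.6% and +0.9% at 30% progression risk with no effect).

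The points on size and on uncertain loss rates stand and limit the weight of the concern. They do not make the rule right. The worst-case binary endpoint is a separate analysis and does not correct this curve or hazard ratio; nor do the two rules conflict. The residual shift from the remedy was smaller than that of Rule 3 in every unequal-loss case run, and keeping deaths is the better main rule once loss tracks worsening.

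**Conclusion.** The concern holds. As written, Rule 3 can count survivors without late spirometry as progression-free to Day 373, and the undefined status leaves open whether Rule 4 applies to them instead. At 6/4 loss about 14 of 300 nintedanib and 10 of 300 placebo patients would each be credited, on average, with about 238 days without an FVC.

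The consequence is modest. Displayed risk is understated in both arms, and the hazard ratio shifts by roughly 1% to 3% towards the arm with more loss in the 6/4, 10/5 and 19/13 patterns. The shift is larger if loss is early, very unequal or related to prognosis, and near zero if loss is equal. All of this rests on assumed loss and event rates.

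The effect is weaker for exacerbation or death (−0.1% to −0.9%) and hospitalisation or death (−0.3% to −1.2%), assuming half of the events after loss are still learned of. The first of these carries only a nominal p-value. The confirmatory analysis is untouched. The rule should be corrected because it is wrong as worded and cheap to put right.

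**What to change.** 1. Limit Rule 3 (Day 373) to event-free survivors assessed in the week-52 window, days 310 to 373 for FVC.
2. Censor other event-free survivors at the last FVC showing no progression. For exacerbation and hospitalisation, use the last contact at which adverse-event or hospitalisation data were collected.
3. State that status in Rules 3 and 4 means event status, and that a contact giving vital status alone does not make a patient event-free.
4. Keep all deaths within 52 weeks as events in the main analysis. This matches the endpoint definition in SAP 5.2.2.2.2 and the use of all available data in Protocol 7.3.2.
5. Add two sensitivity analyses: deaths after missed assessments censored at the last assessment, and the current Rule 3.

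The cost is wording in three SAP tables, derivation code and two runs. No new data are needed, and slightly less follow-up is counted. A small opposite shift remains because late deaths still count (up to +1.5% in the four tabulated patterns and +2.0% in the 20/5 case). No censoring rule is unbiased if loss of spirometry is related to worsening.
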